## **5.2 Recruitment Methods**

Ann Arbor regulatory approval is being requested only for the data analysis portion of AIM 3 (extraction, cleaning, and analysis of AIM 3 outcome data from the VA's electronic health record via the Corporate Data Warehouse). All recruitment, enrollment and intervention activities were completed at the Pittsburgh VA.

Approximately 10,000 Veterans' data will be pulled from the CDW to examine implementation and clinical outcomes. Data to evaluate implementation and clinical effectiveness outcomes will be obtained electronically and securely from already collected administrative databases, using scrambled SSN or Patient ICN to link data together. Data sources will include the CDW, Health Factors (AUDIT-C and Brief Intervention information), Vital Status File to obtain DOB for calculating age of Veterans, and Prescription/Pharmacy information (for data on whether medications for alcohol use disorder were prescribed). Other specific records include: sociodemographics (e.g., sex, gender identity, marital status, indicator of socioeconomic status, race/ethnicity, sexual orientation), past-year diagnoses (Alcohol use disorder diagnosis, Substance use disorder diagnoses, Tobacco use disorder diagnosis, Mental Health disorder diagnosis (Depression, anxiety, PTSD, Bipolar, Psychotic-spectrum)), index of medical complexity (e.g., Charlson index, VA CAN score) utilization of primary care services pre-implementation (2019-2022), during (July 2022 - Dec. 2022) and post-implementation intervention (Jan 2023 - Dec. 2023), referral and utilization of substance use services in the past year (yes/no), and referral and utilization of past-year mental health services (yes/no). Data may also be reviewed within CAPRI/Joint Legacy Viewer (JLV) to allow study team members to look into potential data anomalies from our dataset. In addition, members of the study team may review notes, charts, dates of AUDIT-C administration, etc. to verify the accuracy of our Aim 3 dataset.

## **5.3 Process of Obtaining Informed Consent and Protecting Patient Privacy**

We are requesting a Waiver of Informed Consent and a HIPAA waiver for full access to PHI to complete this work. There will be no participant contact. All data will be stored in VINCI (VA Informatics and Computing Infrastructure) or in a restricted access study folder located on the Ann Arbor VA secure server. All study team members are current on their human subjects protection, HIPAA privacy, and data security training.

In accordance with HIPAA, only approved Study Team Members will have access to protected health information (PHI). Computerized data will be stored in an electronic folder maintained on the VA Server or behind the VA Firewall.

#### **5.4 Inclusion/Exclusion Criteria**

We will include all Veterans with a visit to the Pittsburgh VA primary care during the practice facilitation intervention.

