### **Evaluation of the Practice Facilitation Intervention: Implementation and Clinical Outcomes.**

Aim 3 implementation and clinical-specific outcomes were derived guided by the RE-AIM (Reach, Effectiveness, Adoption, Implementation, and Maintenance) evaluative framework, often used to guide implementation evaluations. RE-AIM will be assessed using EHR data pulled from VA's Corporate Data Warehouse (CDW). The data pull will include data from January 1, 2019 – December 31, 2023, to evaluate these outcomes, which includes the pre-intervention period, the active facilitation intervention period, and the post-facilitation intervention period (i.e., 3-, 6-, and 12-months after active implementation). RE-AIM constructs are defined as follows:

**Reach** of alcohol-related care will be assessed at the patient level using EHR data, pulled from VA's CDW. **Reach** outcomes will be expressed as a rate, with the

denominator (for all outcomes) defined as all Veterans with a visit to the Pittsburgh VA primary care clinic during the practice facilitation intervention. The numerator for each Reach outcome is as follows: the number of Veterans who screened positive for unhealthy alcohol use (AUDIT-C  $\geq$  5) AND had any documented brief intervention, encounters with primary care-mental health integration (PC-MHI), encounters with PACT/ Whole Health clinical pharmacists, specialty addictions treatment (inpatient and outpatient clinic visits for substance use disorder treatment encounters with an accompanying AUD diagnosis), or pharmacotherapy for AUD (any filled prescription for FDA-approved medications: acamprosate, disulfiram, or oral/injectable naltrexone or non-FDA approved effective medications: gabapentin, baclofen, or topiramate) in the 30 days following a positive screen. Denominators will also be derived to represent specific subpopulations (e.g., women, Black and Hispanic Veterans). Rates at the start of the practice facilitation intervention and at 3- and 6-months post intervention will be calculated to examine change in Reach outcomes over time.

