**Adoption** is identified as the percentage of providers from the PC clinic who deliver alcohol-related care when a Veteran screens positive for unhealthy alcohol use. Specifically, we will use data available in the EHR to examine delivery of brief interventions, consults placed to PC-MHI/clinical pharmacists or specialty addictions treatment and providing pharmacotherapy for AUDs at the provider and clinic level. Rates of alcohol-related care pre-intervention (2019-2022), during the course of the practice facilitation intervention (July 2022-December 2022), after the intervention (e.g., 3- and 6-months post intervention (Jan 1, 2023-March 31, 2023, and Jan 1, 2023-June 30, 2023 respectively) will be used to measure whether adoption rates of alcohol-related care increased over time.

**Maintenance** is defined as the extent to which evidence-based alcohol care becomes routine and part of the PC culture (care sustained over time). Reach and Adoption outcomes using EHR data will be assessed at 12-months post intervention (Jan 1, 2023-Dec. 31, 2023) to examine whether high-quality alcohol care was sustained.

**Effectiveness** is defined as the prevalence of unhealthy alcohol use at 12-months post-intervention (Jan 1, 2023-Dec. 31, 2023) as measured by AUDIT-C scores pulled from the EHR. This variable will also be expressed as a rate with the denominator defined as all Veterans with a visit to PC during the practice facilitation intervention (same as for Reach outcomes). The numerator will be the number of Veterans with an encounter in PC who screened positive for unhealthy alcohol use (AUDIT-C  $\geq$  5) at 12-months post facilitation intervention. While it is unlikely that a pilot study will have a measurable

impact on clinical outcomes, measuring effectiveness will serve as pilot data for a larger trial.

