#### **5.7 Data Analysis**

**Implementation Outcomes:** Reach outcomes will be reported descriptively (e.g., percentage of patients with an AUDIT-C  $\geq 5$  who were offered a BI or pharmacotherapy for AUD) and compared pre- (2019-2022) and post-implementation (at 3- and 6-months) to see whether Reach of alcohol care increased over time. Adoption outcomes via EHR will be descriptive, and include percentages, frequencies, and means (SD) of alcohol-related care by provider and clinic to understand whether Adoption of high-quality alcohol-related care increased over time. Descriptives will be examined and compared at the start of Active Implementation and at 3- and 6-months post Active Implementation. Reach and Adoption rates will again be examined at 12-months post Active Implementation and compared to rates at 3- and 6-months to see if high-quality alcohol-related care was sustained (Maintenance). **Effectiveness outcomes:** Effectiveness will be assessed via a time-series analysis, where the intervention site will serve as its own control, and we will investigate whether Veterans' with an encounter in Pittsburgh VA Primary Care during the implementation intervention reduced their drinking 12-months post intervention using AUDIT-C scores in the EHR. Time-series analysis was chosen because historical trend is accounted for in the analytic model, results can be displayed graphically, and the size of the effect can be estimated at different times post

intervention. The outcome (AUDIT-C scores) will be modeled using a regression model with an indicator for practice facilitation (pre- vs. post-), a continuous term for time (days since practice facilitation dissemination) and the interaction between the two. The indicator variable will assess immediate changes in AUDIT-C scores post implementation intervention, while the interaction term will assess if there is a change in the slope of AUDIT-C scores pre- and intervention at 12-months. While there is controversy over whether pilot studies should assess clinical efficacy or effectiveness, we decided to examine it here as a training opportunity and as preparation for a possible hybrid effectiveness-implementation Merit trial investigating practice facilitation as a way to improve alcohol-related care on a larger scale.

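### Selecting the cohort on a visit in July-December 2022 can create a false slope change in the AUDIT-C time series, of either sign, if leaving the clinic is related to drinking

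*Combined protocol and SAP*

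**What the plan says.** The inclusion criterion in Section 5.4 is a single sentence: "We will include all Veterans with a visit to the Pittsburgh VA primary care during the practice facilitation intervention". Section 5.1 (under Adoption) gives the window: "during the course of the practice facilitation intervention (July 2022-December 2022".

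The same Veterans form the Reach "denominator (for all outcomes) defined as all Veterans with a visit to the Pittsburgh VA primary care clinic during the practice facilitation intervention" and are the population of the time-series analysis in Section 5.7. The data run well to either side of the window: "The data pull will include data from January 1, 2019 – December 31, 2023, to evaluate these outcomes". Section 5.7 compares Reach with a 2019-2022 baseline.

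Section 5.7 describes the time series as one "where the intervention site will serve as its own control". Its regression has a pre/post indicator, a continuous time term counted in days from dissemination of the facilitation, and their interaction. It states no patient-level term and no comparison clinic. Section 5.2 names the Vital Status File only as a source of birth dates, and no section says how death, loss to the clinic or a missed screen is handled.

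**The concern.** Entry depends on an event that comes after the whole pre-period. A score from early 2019 is used only if that Veteran was still alive and attending more than three years later. A score from June 2022 needs only a visit within the following six months or so. After the window nobody has to attend to remain in the cohort, and the 2023 scores come from whoever returns and is screened.

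Suppose heavier drinkers leave or die sooner. The earliest pre-period scores then contain too few of them, the pre-period mean rises towards the window, and the post-period mean falls away from it. Section 5.7 reads the interaction term as a change in the slope of AUDIT-C scores, so part of this selection pattern would be reported as an effect of facilitation. The result is meant as pilot data for a larger trial, so a false slope would be carried into its planning.

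**Working it through.** The documents give no effect size, exit rate or re-screening rate, so there is no figure of the plan's to reproduce. The check is what the Section 5.7 model returns when no Veteran's drinking changes.

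**From the documents:** window July-December 2022; data January 2019 to December 2023; model with indicator, time and interaction; one cohort on both sides.

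**Assumed (not in the documents):** a clinic in steady state; a share p of 5% or 10% with AUDIT-C of 5 or more at the window; mean score 6.5 in that group and 1.2 in the rest; constant yearly exit probabilities qH (heavier) and qL (others), mirrored backwards as entry. Pre-period January 2019-June 2022, post-period January-December 2023, window centred on 1 October 2022.

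**Formulas.** At d years from the window centre, on either side, the heavier-drinking share among cohort members with a score is

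w(d) = p(1-qH)^d / [p(1-qH)^d + (1-p)(1-qL)^d], and the mean score is 1.2 + 5.3 × w(d).

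**Example,** p = 10%, qH = 20%, qL = 7%. For January 2019, d = 3.75: 0.80^3.75 = 0.433 and 0.93^3.75 = 0.762, so w = 0.0433/(0.0433 + 0.6856) = 5.9% and the mean is 1.51. At the end of June 2022, d = 0.25: w = 9.7%, mean 1.71. At the end of 2023, d = 1.25: w = 8.4%, mean 1.65. The mean rises to the window and then falls, with no change in anyone's drinking.

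**Least-squares fit of the Section 5.7 model to this no-effect curve** (AUDIT-C points; the 12-month effect is the level term plus one year of slope change):

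| Yearly exit, heavier vs others | p | Slope change per year | 12-month effect, origin Jan 2023 | 12-month effect, origin July 2022 |
|---|---|---|---|---|
| 10% vs 10% | 5%, 10% | 0.000, 0.000 | 0.000, 0.000 | 0.000, 0.000 |
| 10% vs 8% | 5%, 10% | -0.011, -0.020 | -0.013, -0.025 | -0.008, -0.015 |
| 15% vs 7% | 5%, 10% | -0.041, -0.078 | -0.049, -0.094 | -0.028, -0.055 |
| 20% vs 7% | 5%, 10% | -0.063, -0.122 | -0.074, -0.143 | -0.042, -0.082 |
| 7% vs 15% | 5%, 10% | +0.051, +0.095 | +0.066, +0.123 | +0.041, +0.075 |

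The slope change does not depend on the time origin; the 12-month figure does. Moving the origin from January 2023 to July 2022 cuts it by about 40%, and in the 15% and 20% vs 7% rows the level term goes from slightly negative (-0.008 to -0.021) to positive (+0.012 to +0.040).

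**Scale.** A real 1-point reduction confined to 8% of Veterans moves the mean by 0.08 × 1 = 0.08 points.

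**Precision.** Assume 10,000 Veterans, one screen a year, SD 2.2 and independent scores.
- Slope-change SE = √[2.2²/(10,000/12) + 2.2²/(35,000 × 3.5²/12)] = 0.077.
- 12-month SE, origin January 2023 = √[4 × 2.2²/10,000 + (2.2²/35,000)(1 + 12 × 3.25²/3.5²)] = 0.059.

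**Second model as a check.** A separate no-effect simulation used 15% heavier drinkers, means 7 and 2, and exit hazards of 0.1 to 0.3 a year. With the break at July 2022 it gave the same signs: -0.06 to -0.19 points a year when heavier drinkers left faster, +0.06 to +0.28 when lighter drinkers did, and about 0 at equal exit. Patient fixed effects brought the slope change to within about 0.015 of zero in every scenario. A population defined at each calendar time brought it to within about 0.005.

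**The case against.** **Sign and size are not fixed.** A reader might infer that the design has a kink built in that must look like reduced drinking. The documents do not support that. They give no exit rate by drinking level, the artefact is zero at equal exit, and it looks like harm if lighter drinkers leave faster. Section 5.5 says unhealthy use leads to early mortality, which suggests a direction for death but says nothing about Veterans who leave for other reasons. This objection stands.

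**Follow-up is not unconditional.** What carries no condition is cohort membership. A 2023 score still needs a visit and a screen, and Section 5.1 says of the Effectiveness rate: "The numerator will be the number of Veterans with an encounter in PC who screened positive for unhealthy alcohol use". The asymmetry is guaranteed attendance up to the window against selective return after it.

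**Not every baseline figure is affected.** Adoption is counted over providers, and the Effectiveness rate is defined only at 12 months with no baseline, so this point touches neither. For Reach, the Section 5.7 example is a percentage among Veterans with a positive screen. Losing heavier drinkers removes them from numerator and denominator alike, so bias under that definition would need exit to depend on receipt of care.

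**The artefact may be lost in noise.** Under the precision assumptions above, the false slope change is 0.5 to 1.0 SE at 15% vs 7% and 0.8 to 1.6 SE at 20% vs 7%. The 12-month figure from January 2023 passes 2 SE only in the most extreme case (0.143/0.059 = 2.4). It is therefore not established that the plan would report a significant false benefit.

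**Stakes are modest.** Section 5.1 calls a measurable clinical impact unlikely, and Section 5.7 presents the analysis partly as training. That limits the consequences but does not make the estimate interpretable.

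What survives all of this is the anchoring of the pre-period on later attendance, with no stated safeguard.

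**Conclusion.** The point holds in conditional form. Following Sections 5.4 and 5.7 as written can produce a false slope change at the intervention whenever exit is related to drinking, and nothing in the stated model would detect or remove it. Under assumed exit of 15-20% vs 7% a year and 5-10% prevalence, it is about -0.04 to -0.12 points a year. The corresponding 12-month figure is about -0.05 to -0.14 with time from January 2023, or -0.03 to -0.08 with time from July 2022. With a small gap in exit (10% vs 8%) the slope change is at most about -0.02, and with the gap reversed (7% vs 15%) it is about +0.05 to +0.09.

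All of these rest on assumed exit rates, prevalence and group means, a steady-state clinic and constant drinking within person. The baseline Reach comparison uses the same selected cohort, but the size and direction of any bias there are not established.

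**What to change.** Amend Sections 5.4 and 5.7 before extraction and analysis, by one or both of these changes:

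1. **Population defined by period.** For baseline Reach and the AUDIT-C series, count in each period the Veterans seen in primary care in that period, whether or not they returned in July-December 2022.
2. **Within-person term.** For the question of whether these Veterans reduced their drinking, add patient fixed effects to the AUDIT-C model. This needs no wider pull. It removes the artefact when each Veteran's drinking level is stable, but not regression to the mean if heavier drinking prompts the window visit.

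As a sensitivity analysis, apply the same entry rule to July-December 2019, 2020 and 2021 and compare changes over follow-up. The 2021 cohort has only about six months (to June 2022) before facilitation begins. State the break date and time origin of the model, since the 12-month figure depends on the origin.

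**Cost:** rewording and, for the first change, a wider CDW query. The dates lie inside the planned 2019-2023 pull, but the count would exceed the approximately 10,000 Veterans in Section 5.2, and the waiver request in Section 5.3 would need a matching update. The earlier cohorts also need the wider query. There is no patient contact.

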#### **5.5 Risk/Benefit Assessment**

The risk of accessing identifiable data on VINCI (VA Informatics and Computing Infrastructure) or in a restricted access study folder located on the Ann Arbor VA secure server is minimal, while the benefit is potentially great. Veterans who are included in secondary data analysis may benefit indirectly by improvements in their alcohol-related care. In addition, the potential to contribute to scientific knowledge outweighs the minimal risks. Unhealthy alcohol use is common and leads to adverse consequences, including suicide risk and early mortality. VA has invested in alcohol-related care in primary care, however, past implementation gaps have been identified and hypothesized to contribute to lower quality and access. The study is aligned with VA and HSR&D research priorities focused on access to care, suicide prevention, and implementation science and with VA's commitment to providing patient-centered care for unhealthy alcohol use. If effective, the implementation intervention could be scaled throughout VA primary care settings, which may optimize return on VA's large investment in this care.

#### **5.6 Study Evaluations**

Not applicable.

#### **5.7 Data Analysis**

**Implementation Outcomes:** Reach outcomes will be reported descriptively (e.g., percentage of patients with an AUDIT-C  $\geq 5$  who were offered a BI or pharmacotherapy for AUD) and compared pre- (2019-2022) and post-implementation (at 3- and 6-months) to see whether Reach of alcohol care increased over time. Adoption outcomes via EHR will be descriptive, and include percentages, frequencies, and means (SD) of alcohol-related care by provider and clinic to understand whether Adoption of high-quality alcohol-related care increased over time. Descriptives will be examined and compared at the start of Active Implementation and at 3- and 6-months post Active Implementation. Reach and Adoption rates will again be examined at 12-months post Active Implementation and compared to rates at 3- and 6-months to see if high-quality alcohol-related care was sustained (Maintenance). **Effectiveness outcomes:** Effectiveness will be assessed via a time-series analysis, where the intervention site will serve as its own control, and we will investigate whether Veterans' with an encounter in Pittsburgh VA Primary Care during the implementation intervention reduced their drinking 12-months post intervention using AUDIT-C scores in the EHR. Time-series analysis was chosen because historical trend is accounted for in the analytic model, results can be displayed graphically, and the size of the effect can be estimated at different times post

intervention. The outcome (AUDIT-C scores) will be modeled using a regression model with an indicator for practice facilitation (pre- vs. post-), a continuous term for time (days since practice facilitation dissemination) and the interaction between the two. The indicator variable will assess immediate changes in AUDIT-C scores post implementation intervention, while the interaction term will assess if there is a change in the slope of AUDIT-C scores pre- and intervention at 12-months. While there is controversy over whether pilot studies should assess clinical efficacy or effectiveness, we decided to examine it here as a training opportunity and as preparation for a possible hybrid effectiveness-implementation Merit trial investigating practice facilitation as a way to improve alcohol-related care on a larger scale.

Personal identifiers will be required to pull the dataset from VA databases and link data across databases. However, once the data are extracted, merged, and cleaned for analyses, the identifiers (such as scrambled Social Security number, or patient ICN) will be removed from the dataset and replaced with a unique study ID. We will however maintain the linkage between study IDs and scrambled Social Security number or patient ICN in the form of a separate crosswalk file stored in VINCI (VA Informatics and Computing Infrastructure) or in a restricted access study folder located on the Ann Arbor VA secure server until the study is complete. All study team members are current on their human subjects protection, HIPAA privacy, and data security training. Only approved Study Team Members will have access to the data.

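### Reach is compared before and after facilitation as raw percentages of screen-positive Veterans, with no account taken of how severe those Veterans are in each period

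*Combined protocol and SAP*

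**What the plan says.** Section 5.7 (Data Analysis) states that "Reach outcomes will be reported descriptively". Its example is the "percentage of patients with an AUDIT-C" of 5 or more who were offered a brief intervention or medication. These percentages are then reported "and compared pre- (2019-2022) and post-implementation (at 3- and 6-months) to see whether Reach of alcohol care increased over time". The 12-month rates are later set against the 3- and 6-month rates to judge Maintenance. No model, covariate, stratum or standard population is named for Reach.

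The evaluation subsection of Section 5.1 builds the numerator from "the number of Veterans who screened positive for unhealthy alcohol use" (one cut-off, AUDIT-C of 5 or more) and had any of five kinds of care within 30 days. One of these, specialty treatment, covers "visits for substance use disorder treatment encounters with an accompanying AUD diagnosis". The denominator for every Reach outcome is "defined as all Veterans with a visit to the Pittsburgh VA primary care clinic during the practice facilitation intervention", which is not the AUDIT-C group used in Section 5.7. The only subpopulations named are demographic examples.

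Section 5.2 lists AUDIT-C information and "past-year diagnoses (Alcohol use disorder diagnosis, Substance use disorder diagnoses" among the data to be pulled. Neither is given a role in the Reach analysis. AUDIT-C scores are modelled only for Effectiveness.

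**The concern.** The periods are not randomised, and the Veterans who screen positive in each need not be alike. A single cut-off puts a Veteran just above it in the same group as one far above it. If the more severe Veterans receive a given kind of care more often (or less often), the pooled percentage depends on the mix as well as on what the clinic does.

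There is reason to think that the mix could move. The Effectiveness model in Section 5.7 looks for a change in the level and slope of AUDIT-C scores after facilitation. If scores change, the make-up of the positive group can change too, in either direction. A general fall makes positive Veterans milder, whereas Veterans dropping from just above the cut-off to below it leave a more severe group behind.

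At stake is how the trend is read. Aim 3 asks whether facilitation improves the quality of alcohol-related care, and Section 5.7 presents the pilot as preparation for a possible larger trial. A change in mix would enter both the conclusion and the pilot estimates. Reach has no hypothesis test, so no error rate or power figure is affected.

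**Working it through.** **Inputs.** From the documents: one cut-off of 5, a 30-day care window, descriptive percentages, and about 10,000 Veterans in the pull. The number screening positive, the severity mix, care rates by severity and expected Reach are not given, so there is no planned figure to reproduce. All rates below are assumptions, shown over a range.

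**Formula (Section 5.7 denominator).** Let s be the share of positive Veterans in the more severe band, and pH and pL the care rates in the more and less severe bands. Then

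Reach = s × pH + (1 − s) × pL.

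With care unchanged within each band, the change between periods is (s1 − s0) × (pH − pL).

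**Spurious change, any care, s0 = 30%:**

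| pL / pH | Reach before | After, s1 = 35% | s1 = 40% | s1 = 45% |
|---|---|---|---|---|
| 50% / 50% | 50.0% | 50.0% (0.0) | 50.0% (0.0) | 50.0% (0.0) |
| 50% / 60% | 53.0% | 53.5% (+0.5) | 54.0% (+1.0) | 54.5% (+1.5) |
| 50% / 70% | 56.0% | 57.0% (+1.0) | 58.0% (+2.0) | 59.0% (+3.0) |
| 40% / 80% | 52.0% | 54.0% (+2.0) | 56.0% (+4.0) | 58.0% (+6.0) |

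A falling severe share reverses the sign.

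**A less common kind of care.** Assume 30% in the severe band and 8% in the other. At s = 30%, Reach is 0.30 × 0.30 + 0.70 × 0.08 = 14.6%. At s = 40% it is 16.8%, and at s = 20% it is 12.4%. That is 2.2 points either way, or 2.2 / 14.6 = 15% in relative terms.

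**Masking.** Let care truly rise 5 points in each band (40% to 45%, 80% to 85%) while the severe share falls from 40% to 30%. Before: 0.40 × 0.80 + 0.60 × 0.40 = 56.0%. After: 0.30 × 0.85 + 0.70 × 0.45 = 57.0%. Only 1 of the 5 points shows.

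**Effect of standardising.** Holding the pre-period share fixed, the post-period rate is s0 × pH + (1 − s0) × pL. In every cell of the table it equals the pre-period rate, so the change is 0.0. In the masking example it is 0.40 × 0.85 + 0.60 × 0.45 = 61.0%, and the full 5 points appear.

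**Section 5.1 denominator.** With all visitors below the line, Reach is the prevalence of positive screens multiplied by the rate above. At an assumed 52% care rate, prevalence of 5%, 10% or 15% gives 2.6%, 5.2% or 7.8%. Severity bands among positive Veterans do not remove this dependence, so the denominator has to be settled first.

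**The case against.** Several objections have force.

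- **Denominator.** A reader might infer that picking up more mild drinkers must pull Reach down. Under the Section 5.1 denominator it cannot: extra positive Veterans enter only the numerator, which stays level or rises. The case-mix argument applies to the AUDIT-C denominator of Section 5.7 and must be confined to it.
- **Severity as a driver.** A reader might infer that severity is the strongest predictor of care, or that adjusting for it would sharpen the estimates. The documents report no care by score, and standardising can widen intervals where bands are sparse.
- **The AUD condition.** It is tempting to read "substance use disorder treatment encounters with an accompanying AUD diagnosis" as limiting specialty care to Veterans already known to have the disorder. It is a rule for counting an encounter, and the diagnosis may first be made there.
- **Size.** The rates are assumed. With 100 to 500 positive Veterans in a post window (also assumed), the standard error of a 14.6% rate is √(0.146 × 0.854 / n), or 3.5 to 1.6 points, so a 2.2-point shift is 0.6 to 1.4 standard errors. This limits what could be seen in the pilot, but bias does not shrink as numbers grow.
- **Cohort.** Section 5.4 takes only Veterans with a visit during facilitation, which limits turnover. It does not fix the mix: those positive in 2019 and in 2023 need not be the same people or have the same scores.
- **Construct.** Reach is a patient-level descriptive measure, and provider delivery is Adoption. Crude coverage is a legitimate pilot quantity and should stay. But the plan uses its change over time to judge whether care increased, and nothing in the documents separates that from a change in mix.

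**Conclusion.** The point holds as a conditional one. The plan compares crude Reach among screen-positive Veterans across non-randomised periods, names no allowance for severity, and already holds the data to make one. Bias needs both a shift in mix and a care rate that differs by severity. The documents establish neither, so its size and direction are unknown, and for some kinds of care it may be negligible. Over the assumed range the shift is 0.5 to 6.0 points, and zero without a care gap. The documents do not support saying that Reach is biased in a known direction. The change is worth making because it is cheap and the plan would otherwise have no way to tell the two explanations apart.

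**What to change.** 1. Reconcile the Reach denominators in Sections 5.1 and 5.7. The steps below apply to Reach among screen-positive Veterans.
2. Report the distribution of index AUDIT-C scores in each period.
3. Beside each raw rate, show a rate directly standardised to the pre-intervention distribution of index AUDIT-C band. Fix the bands before the rates are examined; the documents give none. State the dates of the reference period too, because the 2019-2022 label overlaps facilitation in July to December 2022.
4. Add AUD diagnosis as a further standardising variable only in a sensitivity analysis, using diagnoses recorded before the index screen. Facilitation offered training on AUD care and may change how the disorder is diagnosed, so standardising on later diagnoses could remove part of its effect. Section 5.2 gives no reference date for past-year.
5. A logistic model followed by marginal standardisation is an acceptable alternative. Its conditional odds ratio is a different quantity and should not replace the standardised rates.

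The cost is a little more analysis and possibly wider intervals where bands are sparse. AUDIT-C and AUD diagnosis are already in the pull, though diagnosis dates relative to the index screen must be kept. No gain in precision is claimed.
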